## 2. INTRODUCTION

PF-06838435 is an adeno-associated viral (AAV) vector designed to drive expression of the human factor IX-Padua (hFIX-Padua) transgene and raise the circulating levels of endogenous factor IX (FIX:C). The Guidance for Industry: Considerations for the Design of Early-Phase Clinical Trials of Cellular and Gene Therapy Products and findings from previous clinical studies with AAV2 and AAV8 vectors were considered in the development of this protocol.

### 2.1. Study Rationale

Data from a recent clinical study of AAV8 gene transfer to participants with severe hemophilia B, sponsored by SJ-UCL (IND 14031), demonstrated that a single peripheral IV infusion of the scAAV8-LP1-hFIXco resulted in 2-12% sustained and long-term vector-derived FIX:C activity levels which were sufficient to improve the bleeding phenotype and reduce the use of regular prophylactic FIX infusions, in some cases completely eliminating the need for these infusions. A recently conducted clinical study using AAV8-hFIX19 in three participants with hemophilia B (IND 15149) at  $1 \times 10^{12}$  and  $2 \times 10^{12}$  vg/kg, resulted in vector-derived FIX:C activity levels of up to 16%. Furthermore, preliminary data of a single peripheral IV infusion of self-complementary BAX-335 (scAAV8.hFIX-Padua) at doses of  $2 \times 10^{11}$  vg/kg,  $1 \times 10^{12}$  vg/kg and  $3 \times 10^{12}$  vg/kg from the ongoing Baxter study (NCT#01687608) also resulted in detectable vector-derived FIX:C activity levels of <1 to ~60% in six participants. These recent clinical studies demonstrate that AAV vectors are well tolerated.

After a single administration of AAV-Spark100-hFIX19-Padua into NHPs, steady-state hFIX activity levels up to 31%, 68%, and 296% of normal were achieved at  $1 \times 10^{12}$ ,  $2 \times 10^{12}$ , and  $5 \times 10^{12}$  vg/kg dose levels respectively, without safety concerns. PF-06838435 and AAV-Spark100-hFIX19-Padua share the same regulatory sequences and encode identical amino acid sequences. Furthermore, studies in mice and in NHPs have shown that these two vectors yield comparable FIX expression. The objective for this study is to evaluate the safety, tolerability, and kinetics of a single administration of PF-06838435 in participants with hemophilia B.

[figure not shown]
### 2.2. Background

#### 2.2.1. Hemophilia B

Hemophilia B, or Christmas disease, is a deficiency of blood coagulation factor IX (FIX) and is recessively inherited due to an X-chromosome mutation carried by females and expressed mainly by males, affecting approximately 80,000 people worldwide. A deficiency of FIX results in bleeding into joints, soft tissue, and muscle. Fatal intracranial bleeding is one of the most serious events that can affect individuals with hemophilia B from neonates to the elderly. Bleeding may be associated with trauma or can occur in the absence of trauma (spontaneous bleeding). Depending on the severity of the bleeding event, it can be life-threatening if not treated appropriately. Factor IX, a serine protease, and factor VIII, a cofactor for FIX, work in concert to activate factor X, a central step in the coagulation cascade. The coagulation cascade has two pathways, the Contact Activation Pathway (Intrinsic Pathway) and the Tissue Factor Pathway (Extrinsic Pathway). The plasma factors are activated in the form of a cascade or “waterfall” one after the other until the soluble

plasma protein, fibrinogen, is transformed into a fibrinous clot. The blood coagulation cascade is illustrated in Figure 2.

**Figure 2. The Blood Coagulation Cascade**

Although platelets are critical to the formation of the hemostatic plug, an effective clot cannot be formed without adequate levels of procoagulant factors. The level of coagulation factors in the plasma of normal individuals range from 50 to 150% (or 50 to 150 IU/dL) of the level in normal pooled plasma. Therefore, clinical features and factor coagulant activity define the severity of the disease.

### 2.2.2. Clinical Manifestations

About 70% of newborn babies with hemophilia have a positive family history. When the diagnosis is not suspected based on a positive family history, affected children present with bleeding from the umbilical stump, prolonged bleeding after circumcision, bleeding following intramuscular immunization, excessive bruising, or rarely with intracranial hemorrhage. Individuals with hemophilia B (circulating factor IX level  $\leq 2\%$  or less than  $\leq 2$  IU/dL) frequently experience bleeding and recurrent spontaneous bleeding events into muscle, soft tissue, and joints (hemarthroses) starting from infancy and throughout adulthood. Examples of bleeding events include intracranial hemorrhage, deep muscle and joint hemorrhage, hematomas, retroperitoneal hemorrhage, bleeding following tooth extraction, post-surgical bleeding, easy bruising, and mucosal bleeding. Musculoskeletal hemorrhages can lead to recurrent hemarthroses and the development of target joints (generally accepted

criterion is a minimum of three bleeds into a single joint within a consecutive three-month period). The inevitable result of such bleeding events is progressive joint damage, leading to disabling arthritis with major effects on physical and psychosocial quality-of-life (QoL) and socio-economic parameters for hemophilia patients. Intracranial hemorrhage is a leading cause of death among individuals with hemophilia, with a mortality rate of up to 50% in adults as well as in children. Intracranial hemorrhage can occur after trauma, but as many as 50% of cases occur spontaneously.

Development of alloantibodies to FIX (ie, inhibitors) is the main complication of any factor replacement therapy. Inhibitory antibodies (usually immunoglobulin G subclass 4 [IgG4]) antibodies that neutralize the procoagulant activity of FVIII or FIX) develop in approximately 3-5% of patients with hemophilia B following exposure to factor replacement therapy. This is a lower frequency than is seen in severe hemophilia A. However, hemophilia B inhibitors may present with anaphylactic responses to infusion of factor IX products. In the presence of inhibitory antibodies, replacement of the missing clotting factor by infusion of FIX becomes less effective. Once replacement therapy is ineffective, acute management of bleeding requires agents that bypass FIX activity. Long-term management of inhibitors in hemophilia A typically consists of eradicating the inhibitor through immune tolerance. However, this method is more problematic and less effective in hemophilia B, especially in association with anaphylaxis. Therefore, development of inhibitors significantly adds to patients' disease burden.

### **2.2.3. Current Therapies for Hemophilia B**

There is no available cure for hemophilia B. Factor replacement therapy purified from human plasma first became available more than four decades ago. Although these factor IX products dramatically improved life expectancy and QoL in the USA and Western Europe, they also resulted in exposure of individuals with hemophilia to blood borne viruses – most significantly hepatitis B (HBV), hepatitis C (HCV), and the human immunodeficiency virus (HIV). HIV sero-conversion studies documented that most individuals with hemophilia were infected between 1978 and 1984. In the U.S.A., most patients with severe hemophilia who were born before 1987 are HIV positive, and many have already died from complications related to the acquired immune deficiency syndrome (AIDS). HCV disease can cause chronic and progressive hepatitis, with eventual development of cirrhosis, and affects the majority of persons with hemophilia B born before 1987. Late complications of HCV are an increasing cause of death in adults who have been infected for decades. In the 1990's, concerns of viral contamination precipitated the development of high-purity virus-inactivated plasma-derived products and genetically engineered recombinant factors with no animal- or human-plasma-derived proteins to minimize the risk of disease transmission. However, these products have not circumvented all of the problems of protein-based therapies.

Current treatment of the disease is based on venipuncture and IV administration of either plasma-derived or recombinant FIX protein replacement home therapy to raise the circulating FIX (FIX:C) activity level to the lowest effective dose to achieve either resolution of bleeding (on-demand treatment) or prevention of bleeding (prophylaxis treatment). Venous access via peripheral veins remains the preferred option for the administration of FIX

products because it allows a large amount of product to be administered frequently as a short infusion using small needles (23-25 gauge). The frequency of administration of FIX products varies among individuals and is tailored to the individual's clinical status, taking into consideration the type of bleed, frequency of bleeding, and goal of treatment for the participant. Both U.S. National Hemophilia Foundation and the World Federation of Hemophilia established recommendations of plasma factor levels and duration of administration for different types of bleeds based on observations over the years. Improvements in FIX replacement therapy have vastly increased the QoL and life expectancy of individuals with hemophilia B; a recently licensed modified FIX agent with extended half-life provided more convenient dosing options. Prophylactic therapy for hemophilia has gradually increased among the adult population in the U.S.A. but is still not universally practiced for several reasons. The expense is prohibitive (an average adult individual with severe hemophilia who elects on-demand treatment to resolve bleeding events spends \$100,000 on factor replacement therapy each year; prophylaxis treatment may triple the yearly cost). Furthermore, children lacking suitable peripheral veins may require central venous access devices (CVADs) for factor infusion, which may result in catheter-related infections and local thrombotic complications that greatly affect the durability of the device for the patient. Reported rates of catheter-related infection due to the residual blood left at the infusion site in hemophilia vary widely; a meta-analysis calculated a pooled incidence of infection of 0.66 per 1000 CVAD days (CI: 0.44-0.97 per 1000 CVAD days). Extended half-life FIX protein products that require less frequent infusions may potentially decrease problems related to venous access.

Gene therapy has been the goal for curative treatment of hemophilia since the initial cloning of the genes more than 30 years ago. As a proposed alternative approach, gene therapy may potentially reduce short-term disability and long-term hemophilic arthropathy, reduce incidence of central nervous system (CNS) bleeding, eliminate the need for indwelling IV catheters or frequent factor infusion, and improve participants' overall QoL and functional independence. Indeed, this prediction has been borne out in the recent SJ-UCL clinical trial, in which all 10 participants who received gene transfer have reduced their use of prophylactic factor products. Additionally, at least 5 of these participants have reduced factor consumption by greater than 90% while remaining free of spontaneous bleeding episodes.

Several features make hemophilia B a good model for gene therapy. The first advantage of hemophilia B as a model for gene therapy is that precise regulation of transgene expression is not required. Therapeutic range is remarkably wide, from >1% to 150% of normal. It is clear, based on data from administration of FIX products into patients with hemophilia B, that levels above  $\leq 150\%$  are not associated with ill-effects since the protein circulates as a zymogen (inactive precursor). Second, as stated, >1% circulating FIX activity levels may provide protection against chronic arthropathy and CNS bleeding. Patients with levels of >5% have mild severity and only rarely experience spontaneous bleeding episodes (although they exhibit abnormal bleeding in response to hemostatic challenges such as surgery or trauma). A third advantage of hemophilia B is the availability of large and small animal models of the human disease. Clearly, animal models are major assets in efforts to establish an experimental basis for gene therapy. In the case of hemophilia, there are well characterized, naturally occurring canine models of the disease and genetically engineered hemophilic mice. Finally, it should be noted that determination of therapeutic

[figure not shown]
efficacy is straightforward and unequivocal in the case of hemophilia B since plasma levels of FIX are easy to measure and correlate well with clinical disease severity.

[figure not shown]
**2.3. Benefit/Risk Assessment**

More detailed information about the known and expected benefits and risks and reasonably expected adverse events of PF-06838435 (fidanacogene elaparvovec) may be found in the Investigator’s Brochure, which is the single reference safety document (SRSD) for this study.

**3. OBJECTIVES, ESTIMANDS AND ENDPOINTS**

Objectives	Endpoints
Primary	

 
The primary objective is to evaluate the safety and tolerability of a single IV infusion of PF-06838435 in hemophilia B participants ≥18 years of age with ≤2 IU/dL [≤2 %] endogenous factor IX [FIX].
 
	
Clinically significant changes from baseline in the following:
 
 
Physical examination
 
Vital signs
 
Laboratory values
 
Incidence of drug-related adverse events (including inhibitor development)
 
FIX incremental recovery (time at maximum activity [Tmax] and percent recovery for FIX activity)
 
Immune response against AAV capsid protein
 
Immune response against hFIX transgene
 
 
For those individuals who develop hepatic transaminases (ALT and/or AST) elevation of approximately 1.5-fold or successively increasing during follow-up above baseline (or vector-derived FIX:C activity levels decline without evidence of FIX inhibitor, accompanied by rising IFN ELISPOTs on PBMCs) after PF-06838435 infusion, treatment with corticosteroids will be instituted. Alternative immunosuppressive

	
therapies will be considered if the initial corticosteroid treatments are not successful.
 
For any individual who reaches >150% vector-derived FIX:C activity levels after the infusion of PF-06838435, laboratory parameters of thrombotic potential will be assessed.

Secondary	

• The secondary objective is to characterize the kinetics of PF-06838435.

	

• Vector-derived FIX:C activity levels:

• Peak

• Steady-state

• FIX antigen levels

CCI
 	

As the primary study objective is the assessment of safety and tolerability of a single IV infusion of PF-06838435, the estimands are defined here only for the secondary objective of the study. This study aims to characterize kinetics of PF-06838435 after a single dose administration in the population of participants meeting study's inclusion/exclusion criteria. The vector-derived endogenous (not affected by intercurrent FIX product infusions) FIX:C activity levels will be characterized by post-treatment population mean. The assessment will be done for each dose of PF-06838435. Since only a single IV infusion of PF-06838435 will be administered during the study, there should be no treatment discontinuations. There may be missing data, including those from participants lost to follow-up, but it is anticipated to be rare. The handling of missing data is discussed in the Statistical Analysis Plan (SAP).

#### 4. STUDY DESIGN

##### 4.1. Overall Design

This is a Phase 1/2a, open-label, non-randomized, dose-escalation and multi-center study to evaluate the safety, tolerability, and kinetics of a single IV infusion of PF-06838435 in hemophilia B participants with  $\leq 2$  IU/dL [ $\leq 2\%$ ] endogenous factor IX [FIX]). Approximately 20 evaluable participants will be dosed with a single IV infusion of PF-06838435 at one of three different dose levels, see Schema in [Section 1.2](#).

##### 4.1.1. Initial Sequence of Enrollment

The following two staggering strategies are employed in this study based on the recommendation from The Guidance for Industry: Considerations for the Design of Early-Phase Clinical Trials of Cellular and Gene Therapy Products:

1. The first two participants at the starting dose level ( $5 \times 10^{11}$  vg/kg) will be infused with PF-06838435 at least 2 weeks apart; and
2. There will be at least 8 weeks of staggering between each dose level. At least 8 weeks of safety data from at least 3 out of 5 participants in a given dose level will undergo review by an independent DMC prior to dosing the first subject in the next dose level.

A schematic of the study design is presented as [Figure 1 Section 1.2](#)

CCI

### 4.1.3. Dose Escalation and Expansion

#### 4.1.3.1. Initial Dose Escalation

Dose escalation and dose level expansion strategies are employed in the study based on vector-derived FIX activity levels as well as any immune responses against AAV capsid. There will be no dose escalation if at least 3 participants in any dose level achieve steady-state vector-derived FIX activity levels of  $\geq 40\%$ . Steady-state levels are based on 2 separate vector-derived FIX:C activity level measurements (at least two weeks apart) starting from Week 8-12 with adequate washout (ie, 96 hours for factor IX plasma-derived [pd]- or r-FIX and up to 168 hours for extended half-life recombinant factor IX (rFIX) from FIX product.

Dose escalation will occur under the following scenarios:

1. If neither of the first two participants in a given dose level achieve detectable steady-state vector-derived FIX activity levels above their baseline, then escalation to the next dose level will occur, provided there are no safety concerns; or
2. If less than 3 evaluable dosed participants in a given dose level achieve steady-state vector-derived FIX activity levels between 3% to 40% of normal, then escalation to the next dose level will occur, provided there are no safety concerns.

At least 8 weeks of safety data from at least 3 out of 5 participants in a given dose level will undergo review by the independent DMC prior to infusing the first participant in the next dose level (See [Section 4.1.1](#) for staggering strategy). The decision to dose escalate will require the agreement of Pfizer and DMC.

Dose level expansion will occur for the following scenarios:

1. If at least one of the first two participants at the low or middle dose level achieve steady-state vector-derived FIX activity level above their baseline, then up to an initial 5 evaluable participants will be dosed at the respective dose.
2. If one or both of the first two participants in any dose level achieve circulating vector-derived FIX activity levels above their baseline (without using any FIX product) but with a decline to their baseline levels due to an immune response to vector capsid that is NOT well-managed by corticosteroids, then dose escalation will not occur, and instead up to a total of 5 evaluable participants will be dosed at the respective dose.

3. If at least 3 out of 5 participants in the given dose level [scenario “1” above] achieve steady-state vector-derived FIX activity levels above 5%, then the initial dose level may be expanded up to 10 evaluable participants.
4. If at least 6 out of 10 participants in the given dose level [scenario “3” above] achieve steady-state vector-derived FIX activity levels above 5% after the initial dose-level expansion, then the initial dose level may be further expanded by up to 10 additional participants (a total of 20 evaluable participants would be allowed).

CCI

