### Rationale

Adeno-associated virus vector (AAV) vectors have been administered in more than 100 gene transfer clinical trials for a wide range of indications, including several studies for hemophilia B, and have demonstrated a good safety profile. Importantly, data from a recent clinical study of AAV8 gene transfer to participants with severe hemophilia B, sponsored by St. Jude Children's Research Hospital – University College London (SJ-UCL), demonstrated that a single peripheral intravenous (IV) infusion of the self-complementary AAV8-LP1-hFIXco resulted in sustained and long-term circulating vector-derived factor IX (FIX:C) activity levels of 2-12%, which were sufficient to improve the bleeding phenotype and reduce the use of regular prophylactic factor IX (FIX) infusions, in some cases completely eliminating them^3. The previous Sponsor also conducted a study of an AAV8 vector for hemophilia B (AAV8-hFIX19, IND 15149) study was recently conducted. In that trial, the vector was well tolerated and all three dosed participants experienced initial increases in vector-derived FIX:C activity levels. For two of the three participants, expression was short-lived (~2-4 months), likely due to an immune response to some vector component, despite the initiation of an immunosuppressive regimen; for the third participant, expression was longer-lived (~18 months), but trended inexorably downward despite the immunosuppressive therapy. The objective of this study is to evaluate the safety, tolerability, and kinetics of a single IV infusion of PF-06838435 in hemophilia B participants with  $\leq 2$  International Units (IU)/dL [ $\leq 2\%$ ] endogenous factor IX levels.

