3.1. Overall Study Design and Plan

This is a Phase 1/2a, open-label, non-randomized, dose-escalation and multi-center study to evaluate the safety, tolerability, and kinetics of a single intravenous infusion of PF-06838435 in hemophilia B subjects with ≤ 2 IU/dL [$\leq 2\%$] endogenous factor IX [FIX]).

Approximately 15 evaluable subjects will be dosed with a single intravenous infusion of PF-06838435 at one of three different dose levels.

Subjects will provide informed consent and then undergo screening assessments up to 6 (± 2) weeks prior to PF-06838435 infusion on the Dosing Day (Day 0). All dosed subjects will undergo safety observation for a total of 52 (± 2) weeks after PF-06838435 infusion (see the Schedule of Events). Subjects who complete 52 (± 2) weeks (End-of-Study) will be encouraged to enroll in an extension study evaluating the long-term safety of PF-06838435 for up to an additional 5-year long-term follow-up (LTFU).

The administration of PF-06838435 to the first two subjects in the starting dose level will be staggered by at least two (2) weeks to ensure safety. Additionally, at least eight weeks of safety data from at least three (3) out of five (5) subjects in a given dose level will undergo review by an independent Data Monitoring Committee (DMC) prior to dosing the first subject in the next dose level.

There will be no dose escalation if at least three (3) subjects in any dose level achieve steady-state vector-derived FIX activity levels of $\geq 40\%$. Steady-state levels are based on an average of vector-derived FIX:C activity level measurements starting from Week 12 with adequate washout (i.e., 96 hours for pd- or r-FIX and up to 168 hours for extended half-life rFIX) from FIX product.

Originally, up to five (5) evaluable subjects may be dosed in each dose level. An initial dose level may be expanded up to ten (10) evaluable subjects if at least three (3) out of five (5) subjects achieve detectable steady-state vector-derived FIX activity levels above 5%. If, after the above initial dose-level expansion, at least six (6) out of ten (10) subjects achieve detectable steady-state vector-derived FIX activity levels above 5%, then further dose level expansion of up to ten (10) additional evaluable subjects would be allowed (a total of up to twenty evaluable subjects at the starting dose level of 5×10^{11} vg/kg).

The decision to dose escalate will require the agreement of the Sponsor and the DMC.

CCI
[Redacted text block]

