10.2. Vector-derived FIX:C Activity

The analysis of peak FIX:C activity will utilize summary descriptive statistics and individual subject listings and FIX Activity graphs will be presented and summarized by dose group for all vector-derived FIX:C activities by scheduled time-point.

FIX:C activity versus time will be plotted for each subject and the geometric mean concentration versus time plotted by dose group. Steady-state geometric means will be calculated for each individual and summarized for the whole group by dose group will be calculated.

CCI [REDACTED]
[REDACTED]
[REDACTED]
[REDACTED]

CCI [REDACTED]
[REDACTED]
[REDACTED]
[REDACTED]

12. Interim Analysis

No formal interim analyses are planned.

13. References

1. Giangrande P. Haemophilia B: Christmas disease. *Expert Opin. Pharmacother.* 2005; 6:1517-1524.
2. Srivastava, A, A K Brewer, E P Mauser-Bunschoten, N S Key, S Kitchen, A Llinas, C A Ludlam, et al. 2012. "Guidelines for the Management of Hemophilia." *Haemophilia : the Official Journal of the World Federation of Hemophilia* 19 (1): e1–e47.
3. Roberts, H R, and M E Eberst. 1993. "Current Management of Hemophilia B." *Hematology/Oncology Clinics of North America* 7 (6): 1269–80.
4. National Hemophilia Foundation. 2007. MASAC Document #179: Recommendation Concerning Prophylaxis.
5. Colvin, B T, J Astermark, K Fischer, A Gringeri, R Lassila, W Schramm, A Thomas, J Ingerslev, Inter Disciplinary Working Group. 2008. "European Principles of Haemophilia Care." *Haemophilia : the Official Journal of the World Federation of Hemophilia.* Blackwell Publishing Ltd.
6. Nathwani, Amit C, Ulreke M Reiss, Edward G D Tuddenham, Cecilia Rosales, Pratima Chowdary, Jenny McIntosh, Marco Della Peruta, et al. 2014. "Long-Term Safety and Efficacy of Factor IX Gene Therapy in Hemophilia B." *The New England Journal of Medicine* 371 (21): 1994–2004.
7. Buchlis, George, Gregory M Podsakoff, Antonetta Radu, Sarah M Hawk, Alan W Flake, Federico Mingozzi, and Katherine A High. 2012. "Factor IX Expression in Skeletal Muscle of a Severe Hemophilia B Patient 10 Years After AAV-Mediated Gene Transfer." *Blood* 119 (13): 3038–41.
8. Mingozzi, Federico, and Katherine A High. 2013. "Immune Responses to AAV Vectors: Overcoming Barriers to Successful Gene Therapy." *Blood* 122 (1): 23–36.
9. Mingozzi, Federico, and Katherine A High. 2011b. "Immune Responses to AAV in Clinical Trials." *Current Gene Therapy* 11 (4): 321–30.

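### Neither definition of steady-state FIX:C tests for stability, so falling or later-lost expression can be counted or summarised as steady state

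*Protocol*

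**What the plan says.** Steady-state vector-derived FIX:C is a named secondary endpoint (Protocol Section 3, SAP Section 3.2.2). It is also the variable in the dose-escalation and dose-level expansion criteria.

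- **Protocol Section 4.1.3.1:** "Steady-state levels are based on 2 separate vector-derived FIX:C activity level measurements (at least two weeks apart) starting from Week 8-12", after adequate washout from FIX product. The section does not say how the two values are combined or how much they may differ.
- **Expansion criteria, same section:** scenario 3 begins "If at least 3 out of 5 participants in the given dose level" and allows expansion to 10 participants if their steady state is above 5%. Scenario 4 repeats this with 6 of 10 and allows up to 20. Both say the dose level may be expanded.
- **SAP Section 3.1:** "Steady-state levels are based on an average of vector-derived FIX:C activity level measurements starting from Week 12 with adequate washout". No end of the window is given.
- **SAP Section 10.2:** "Steady-state geometric means will be calculated for each individual and summarized for the whole group by dose group".
- **Estimand, Protocol Section 3:** "FIX:C activity levels will be characterized by post-treatment population mean".
- **PK analysis set (Protocol Section 9.3, SAP Section 4.3.3):** requires that steady state can be acceptably determined, without saying what is acceptable.

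**The concern.** A level is steady if it has stopped changing. Both rules replace that test with a calendar: a reading qualifies because of its week and its washout, whatever the readings around it show.

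The plan itself expects that expression may fall. The Synopsis rationale says of two of three participants in an earlier AAV8 trial that "expression was short-lived (~2-4 months), likely due to an immune response to some vector component", and that the third declined over about 18 months. Appendix 6 describes T-cell destruction of hepatocytes as a potential effect of PF-06838435, presenting with rising liver tests and/or falling FIX activity. Section 4.1.5 lists a FIX:C decline without inhibitor as a reason for which corticosteroids may be added.

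Two uses of the term are at stake. A participant whose level is falling can count toward expansion. And the secondary-endpoint table can report as steady state a figure well above where participants ended, with no count of those who lost expression beside it.

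**Working it through.** The plan states no figure for this point (the study is descriptive), so there is nothing of its own to reproduce. The check scores constructed records by each rule.

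**Inputs.** The scheduled FIX activity visits from Week 12 are Weeks 12, 14, 16, 18, 22, 26, 32, 42 and 52, nine in all (Schedule of Activities). Unscheduled visits are left out because SAP Section 4 keeps them out of summary tables. The Week 12 window of SAP Section 3.1 is taken to apply to the geometric mean of SAP Section 10.2. All levels and rates of decline are assumptions.

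**1. Timing of loss in the earlier trial.** 2 × 52/12 = 8.7 weeks and 4 × 52/12 = 17.3 weeks. This overlaps the weeks in which the protocol rule takes its two readings.

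**2. Protocol rule.** Take 12% at Week 10 and 6% at Week 12. The readings are two weeks apart and both exceed 5%. Their mean is (12 + 6)/2 = 9%. The participant can count as above 5% although the level has halved in two weeks. A smoother case: 12% at Week 8 with a 4-week half-life gives 12 × 0.5^(2/4) = 8.5% at Week 10, which also qualifies, and 12 × 0.5^(18/4) = 0.53% at Week 26. The missing combining rule matters too: 9% and 1.5% average 5.25%, which passes on the mean but not if both must exceed 5%.

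**3. SAP rule, early loss.** Let the first record continue with 3% at Week 14 and 1% from Week 16. The nine values are 6, 3 and seven of 1. The arithmetic mean is 16/9 = 1.8% and the geometric mean is 18^(1/9) = 1.4%. Here the SAP value does reflect the loss.

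**4. SAP rule, loss during the study.** Take k visits at 30% and 9 − k at 2%. The arithmetic mean is [30k + 2(9 − k)]/9 and the geometric mean is exp{[k ln 30 + (9 − k) ln 2]/9}.

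| Last visit at 30% | k | Arithmetic mean | Geometric mean (SAP 10.2) | Week 52 |
|---|---|---|---|---|
| Week 16 | 3 | 11.3% | 4.9% | 2% |
| Week 22 | 5 | 17.6% | 9.0% | 2% |
| Week 26 | 6 | 20.7% | 12.2% | 2% |

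**5. SAP rule, slow decline.** Take 12% at Week 8 with a 16-week half-life. The nine visit weeks average 234/9 = 26, so the geometric mean equals the Week 26 level: 12 × 0.5^(18/16) = 5.50%. Week 52 is 12 × 0.5^(44/16) = 1.78%.

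**6. Loss of washed-out samples.** Note 16 of the Schedule of Activities lets prophylaxis resume on the investigator's advice, and SAP Section 4 imputes nothing. With 12% at Week 8 and an 8-week half-life, the geometric mean over nine visits is 12 × 0.5^(18/8) = 2.52%. If readings below 2% drop out for lack of washout (an assumption), six visits remain with mean week 108/6 = 18. The value becomes 12 × 0.5^(10/8) = 5.05%, while the actual Week 52 level is 12 × 0.5^(44/8) = 0.27%.

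**The case against.** Four arguments on the other side carry weight.

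- **The endpoint averages over time.** A reader might infer that the secondary endpoint is overstated as a rule. The documents do not support that. The SAP average has no stated end, so later lows enter it, and the geometric mean weighs them heavily (1.4% in step 3, 4.9% in the first row of step 4). The estimand is a post-treatment mean, and a mean above the last value is not in itself an error. What stands is narrower: the figure is labelled steady state, and it can sit well above the end-of-study level when loss comes mid-study or slowly, or when later samples are excluded.
- **The expansion criteria are permissive.** A reader might infer that falling expression triggers expansion. The text says may. Section 4.1.3.1 bases its strategies on capsid immune responses as well as FIX activity, and scenario 2 addresses decline to baseline in the first two participants. An independent DMC reviews safety data. No early reading can foresee later loss. But scenario 2 is not tied to the 5% criteria, and a fall already visible between the two readings is not screened out.
- **Loss would not be hidden.** Per-subject FIX:C curves, joint FIX:C and liver-test figures, listings and T-cell narratives would show it. They do not change the tabulated steady-state value or give a count of participants who lost expression.
- **The precedent is another vector.** A reader might infer from the earlier trial, where none of three participants kept stable expression, that the same is expected here. It used AAV8-hFIX19. The same rationale reports sustained expression in a different AAV8 trial, and Appendix 6 says the immune reaction has responded to corticosteroids, including in the Phase 1/2a study. The precedent shows a known failure mode, not its frequency.

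Text in Section 4.1.3 and after SAP Section 10.2 is blacked out and may add detail.

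**Conclusion.** The point holds in this form: in the visible text neither rule contains a stability condition. Under the protocol rule, expression that is halving can count as a steady state above 5%. Under the SAP rule, loss from 30% to 2% after Week 22 or Week 26 is summarised as 9.0% or 12.2%, against 2% at Week 52, and slow decline as 5.50% against 1.78%. These sizes rest on constructed profiles, complete scheduled visits except in step 6, and the Week 12 window applying to SAP Section 10.2. They do not estimate how often this happens. No error rate or power is affected, since no hypothesis is tested. The change is worth making because Protocol Section 9.2 says the study is meant to inform dose selection.

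**What to change.** In the SAP, which Protocol Section 9.4 says is finalised before database lock:

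1. Use one steady-state derivation, stating the window, how readings are combined and how samples without washout are treated.
2. Pre-specify a criterion for change between qualifying readings. The documents give no assay variability figure, so the sponsor must supply the limit. The sponsor should also state how recovery after a treated decline is classified.
3. Derive a maintained / not maintained flag for each participant.
4. By dose group, report the number in each category and the Week 52 washed-out FIX:C beside the steady-state geometric mean. Keep the planned mean for all PK-set participants.
5. Reconcile the protocol and SAP definitions so that the term in the expansion criteria has one meaning. How those criteria are used remains with the sponsor and the DMC.

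The cost is wording in two documents and one derived flag, all from data already collected. The summary may look less favourable.
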